The full range of sedation effects is achieved by administering the drug at a rate so that no sedation is present initially, with levels of sedation present that allow the naming task to be performed during the bulk of the infusion period. By the end of the infusion period sedation appropriate for the therapeutic procedure is present, namely, unresponsiveness to voice. Analysis of subsequent recognition memory and sedation at the time of encoding allows one to determine the time of picture presentation at which 50% memory effect occurs and compare it to the time at which 50% sedation occurs. The larger the separation between these two dose-response points, the greater are the amnesic properties present for the drug. This is illustrated below using exemplars from volunteer studies we have previously conducted.

[figure not shown]

FIG 1 Infusion of a typical **sedative** drug (**thiopental**) over 10 minutes, during which time 60 pictures were shown. As time increased (higher picture number), sedation increased, and fewer responses occurred (dark dots). Response data (response to picture task during infusion (yes/no) and subsequent recognition of picture, gray crosses) were fitted to regression curves. For sedative drugs, the subsequent lack of recognition memory parallels the increase in sedation, i.e. there was no specific amnesic effect (**a small difference in 50% effect** (horizontal black line) for memory and sedation)

[figure not shown]

FIG 2 Infusion of propofol (a typical **amnesic** drug) over 10 minutes, during which time 60 pictures were shown. As time increased (higher picture number), sedation increased only at the end of infusion (dark line). The hallmark of amnesia is the lack of subsequent recognition which begins well before any increase in sedation (dark line, **a large difference in 50% effect for memory and sedation**).

As there is substantial evidence that propofol is amnesic in adults and propofol is the most common sedative agent used for pediatric procedures, we wish to initially test the drug ramping paradigm as a measure of amnesic effect using propofol in pediatric patients. The main goal of this study is to determine the feasibility of patient accrual and ability to define the relationship of amnesia to the level of sedation.

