7.0 ASSESSMENT/EVALUATION PLAN

The recognition memory task will consist of simple line drawings selected from a larger stimulus data base (<http://crl.ucsd.edu/experiments/ipnp/method/getpics/getpics.html>) based on their age appropriateness and identifiability by children in the target age range. Stimulus items are presented by means of a bound stimulus book with one black and white line drawing presented on each page. A brief test will be performed to familiarize the child with performing the picture naming task, using different pictures from those that will be shown in the study. If the child is not able to cooperate sufficiently with the test task, then he/she will be withdrawn from the study and propofol will then be administered as per normal clinical practice for their procedure. If sedation will be needed, propofol infusion will be started at a rate to deliver 3mg/kg over a 10 minute period. During this learning phase of the study, pictures will be presented to the participant and the participant will be asked to name each object pictured with accuracy and non responses will be recorded by the examiner. If sedation is being given, the drug infusion rate will be adjusted according to clinical observation (e.g. excessive sedation/no drug effect apparent) so that the patient will be appropriately sedated for the planned procedure by the end of the 10 minute infusion period. After conclusion of the initial infusion, propofol will be administered as per usual practice. Following the procedure after awakening in the PACU, when no apparent sedation is

Amended: 6/10/13

MEMORIAL SLOAN-KETTERING CANCER CENTER IRB PROTOCOL

IRB#: 12-006A(5)

present, or after a similar time period, if no sedation was used, the picture recognition phase of the study will be performed. Patients will again be presented the original pictures with an equal number of pictures not seen during the infusion phase. The order of pictures in the learning (propofol infusion) and recognition phases(PACU) will be the same for every patient. The child will indicate whether the picture was seen before (yes/no). The study is complete. The child will be discharged form the PACU as per standard clinical criteria."

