where $\alpha > 0$ and $\beta > 0$ are the scale and shape parameters, respectively, and $x \geq 0$. (35) The constant of 0.5 assumes a 50-50 chance of a random response in a psychophysical task. Conventionally, the median of $F(x)$ is called the “threshold” of the underlying psychometric function (the value of x for which $F(x) = 0.5$). Because of the assumed 0.50 constant in $G(x)$, and the 0.5 times the median of the Weibull, the threshold estimate is the x value of an overall 75% response probability given the Weibull parameters. The threshold of a psychometric function generally represents the strength of stimulus that elicits a sensation or a noticeable difference. In this case the sedation threshold represents the time value of x when sedation is actuated. We will estimate one sedation curve and its corresponding threshold for each child.

MEMORIAL SLOAN-KETTERING CANCER CENTER IRB PROTOCOL

IRB#: 12-006A(5)

2. "Memory threshold": When the anesthesia has worn off at approximately 1 hour later, the child will be presented with another list of 120 pictures with half having been presented during the initial infusion of propofol. At the presentation of each picture, the child will be asked whether or not he/she remembers having seen it previously. Each response will be coded as correct (true positives and true negatives) or incorrect (false positives and false negatives). A curve may be fitted to the memory recognition data to estimate the average memory decay function for each child. In Figure 1 and 2 this is represented as the light gray curve, which can be modeled as $1 - G(x)$ above. Similarly, a threshold represents the time value (picture number) when memory fades below threshold.

The *sedation* threshold in Figure 1 is at image 25 (250 seconds), while the *memory* threshold is at approximately image 28 (280 seconds). This 30-second / 3 picture difference is taken to represent that sedation occurs concurrently with memory decay. Alternatively, in Figure 2, the *sedation* threshold is at image 58 (580 seconds) while the *memory* threshold is approximately at image 40 (400 seconds). This larger difference of 180 seconds / 18 pictures is a measure of how much sooner amnesia occurred in this instance than sedation. In this latter case, a measurable amnesic effect of 180 seconds can be inferred from the two threshold values.

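### The memory curve's fixed 0.5 floor is not the chance level for yes/no recognition of shown pictures, and the plan does not say which responses enter the curve or how false positives are used

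*Combined protocol and SAP*

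**What the plan says.** Section 11.0, Aim 2 (Memory threshold) states that "the child will be presented with another list of 120 pictures with half having been presented during the initial infusion of propofol". Section 7.0 agrees on the ratio: "Patients will again be presented the original pictures with an equal number of pictures not seen during the infusion phase". On scoring, Section 11.0 says "Each response will be coded as correct (true positives and true negatives) or incorrect (false positives and false negatives", and continues: "A curve may be fitted to the memory recognition data to estimate the average memory decay function for each child". The horizontal axis is time or picture number: "a threshold represents the time value (picture number) when memory fades below threshold".

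The model, stated for the sedation curve and carried over to memory, is G(x) = 0.5 + 0.5·F(x) with F a Weibull distribution function. The 0.5 is justified as a 50-50 random response, and the threshold is taken where the overall probability is 75%. The memory curve is said to be obtainable as 1 − G(x).

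Section 3.0 describes the aim as to "determine the time of picture presentation at which 50% memory effect occurs", and the Figure 1 caption describes the plotted memory data as "subsequent recognition of picture, gray crosses".

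No sentence restricts the memory curve to shown pictures, gives novel pictures a position on the axis, or assigns a use to false positives.

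**The concern.** Three parts of the specification do not fit together.

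- **Axis.** Presentation time exists only for shown pictures. Half of the recognition answers have none.
- **Scoring and floor.** A single correct/incorrect code with chance at 0.5 suits accuracy over shown and novel pictures together. It does not suit the hit rate on shown pictures, where the no-memory level is the child's tendency to say yes.
- **Shape.** As written, 1 − G(x) starts at 0.5 and falls to 0. A hit rate should fall from near 1 to the false-positive rate.

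The memory threshold is one of the two terms in the Aim 2 one-sample test. Aim 1 counts a child as feasible only if usable curve parameters result. If the floor is wrong, the threshold moves by an amount that depends on the child's response bias. Eligible ages run from 4 to 14 years, so bias may well vary between children, although the documents give no rates.

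**Working it through.** **The plan's own figure.** The one-sample t-test with n = 35, mean 0.50, SD 1.0 and two-sided 0.05 has exact power 0.8195 against the stated 80%. That figure is not in dispute. The question is what goes into the difference being tested.

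**Share of answers without a presentation time.** 60 of 120 = 50%. One picture every 5 seconds for 10 minutes gives 600/5 = 120 shown, not 60, but with equal numbers of novel pictures the share is still 50%.

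**Where 0.5 is the chance level.** Take a child with no memory who says yes with probability f to every picture.
- Shown and novel pooled: 0.5·f + 0.5·(1 − f) = 0.5 for any f.
- Shown only: proportion correct = f, i.e. 10%, 20% or 30% for f = 0.10, 0.20, 0.30.

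So 0.5 is right for shown pictures only if f = 0.5.

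**Effect on the threshold, shown pictures only.** Assumptions not in the documents: shape 4, f from 0.10 to 0.30, hit ceiling c of 0.98 or 1.0, and 60 shown pictures. The true half-way threshold is set at picture 40, as in the plan's Figure 2 example. The true hit rate is

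h(x) = f + (c − f)·exp[−ln 2·(x/40)^4].

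First, the picture at which this crosses 75%, by hand. Put s = (0.75 − f)/(c − f); then x = 40·(−log2 s)^(1/4). With c = 1:
- f = 0.10: s = 0.65/0.90 = 0.722, x = 40·0.470^(1/4) = 33.1
- f = 0.20: s = 0.55/0.80 = 0.688, x = 40·0.541^(1/4) = 34.3
- f = 0.30: s = 0.45/0.70 = 0.643, x = 40·0.637^(1/4) = 35.7
- f = 0.50: s = 0.5, x = 40.0

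Second, an expected-likelihood fit of 0.5 + 0.5·exp[−(αx)^β], the falling curve with the plan's floor, reading the threshold at 75%:

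| f | c = 0.98 | shift | c = 1.0 | shift |
|---|---|---|---|---|
| 0.10 | 29.7 | −10.3 | 32.0 | −8.0 |
| 0.20 | 30.9 | −9.1 | 33.3 | −6.7 |
| 0.30 | 32.6 | −7.4 | 34.8 | −5.2 |

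The fits fall earlier than the 75% crossings because the curve cannot go below 0.5, so late misses pull it to the left. With the floor set to f and the upper level to c, the fit returns 40.0. With the floor set to f but the upper level held at 1 when c = 0.98, it returns about 38.8.

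**Yardstick.** 5.2 to 10.3 pictures exceeds the plan's 3-picture example of concurrent loss and is 29% to 57% of its 18-picture amnesic example (5.2/18 and 10.3/18).

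**Dependence on shape.** For f = 0.10 and c = 1 the 75% crossing is 40·0.470^(1/2) = 27.4 at shape 2 and 40·0.470^(1/8) = 36.4 at shape 8, against 33.1 at shape 4.

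**If 1 − G(x) were taken literally.** Its half-way level is 0.25. With c = 1, the hit rate reaches 0.25 at:
- f = 0.10: s = 0.15/0.90 = 0.167, x = 40·2.585^(1/4) = 50.7
- f = 0.20: s = 0.05/0.80 = 0.0625, x = 40·4^(1/4) = 56.6
- f = 0.30: never

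That reading makes the threshold late, not early.

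**The case against.** The strongest reply is that the plan never puts novel pictures on the curve. The scoring sentence is a per-response rule, and for a shown picture correct means a hit and incorrect a miss. Section 3.0, the Figure 1 caption and the picture-number axis all point to shown pictures only. This stands. A reader might infer that half the data will be forced onto the curve and distort it, but the documents do not support that as a finding. A trial calculation with pooling moved a threshold of 40 by −24.6 to +21.2 pictures. Those figures need an invented position for each novel picture (spread evenly over 1 to 60) and assumed correct-rejection rates of 0.60 to 0.95. The shift was near zero (−1.4) at a rate of 0.75. They should not be quoted as the size of the problem.

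A second reply is that the 0.5 constant is disclosed as an assumption. Disclosure does not make it the right chance level for a yes/no answer about a shown picture, and the novel pictures supply the data to replace it.

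A third is that a floor for each child costs precision, when Section 9.0 already doubts whether estimates will be stable and Section 11.0 raises a ten-events-per-parameter rule. This is a fair cost and is dealt with in the fix.

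A fourth is that feasibility is the primary aim and Section 9.0 calls it premature to expect a reliable difference. That lowers the stakes. It does not remove them, because Hypothesis 1 is stated and powered, and feasibility itself depends on usable curve estimates.

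**Conclusion.** The concern holds in a limited form. The analysis set and the role of the novel-picture answers are not stated. On the reading that the documents favour, shown pictures only, the fixed 0.5 floor and 75% threshold are wrong unless a child's false-positive rate happens to be 50%. The literal 1 − G(x) form does not describe the data either.

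With a falling curve on a 0.5 floor, the memory threshold comes out about 5 to 10 pictures early. On the plan's example scale of 10 seconds per picture that is 50 to 100 seconds; at 5 seconds per picture it is 25 to 50. The size rests on the assumed shape, false-positive rates and ceiling.

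The error lies in the direction of Hypothesis 1, but a reader should not conclude that the Aim 2 test is certain to favour it. Literal use of 1 − G(x) would push the other way. The same constant is also applied to the sedation curve, whose own error was not examined here and could add to or offset this one.

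**What to change.** - State that the memory curve is fitted to hit or miss on shown pictures only, against presentation time.
- Replace 1 − G(x) and the fixed constant with a decreasing Weibull curve whose lower asymptote is the child's false-positive rate on the novel pictures. Plug in the observed rate, or shrink it across children in the planned NLMIXED model if single-child estimates are unstable.
- Define the memory threshold as the time half-way between the upper level and that floor, and say how the upper level is set.
- State that true negatives and false positives serve only to estimate the floor.
- Reconcile the picture count: "another list of 120 pictures with half having been presented during the initial infusion of propofol" implies 60 shown, while the 5-second schedule over 10 minutes implies 120.

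The cost is a changed coding rule and model statement; all the data are already to be collected. The drawback is that the floor carries error or adds a parameter. With 60 novel pictures the standard error of a plugged-in rate is √[f(1 − f)/60], or 0.039, 0.052 and 0.059 at f = 0.10, 0.20 and 0.30. That is small beside the distance from those rates to 0.5.

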2.0 OBJECTIVES AND SCIENTIFIC AIMS

1. The primary objective is to determine the feasibility of using the visual picture naming task in pediatric patients in the clinical setting. Feasibility will be defined as being able to accrue an average of 2 patients a week who successfully name and recognize sufficient numbers of pictures so that the thresholds for sedation and memory can be determined in each individual (as described in Section 11.0, Aim 1).
2. The strength of propofol amnesia (the effect of propofol on memory not related to sedation) will be estimated as a difference between thresholds for amnesia (loss of memory) and sedation (loss of verbal responsiveness)

MEMORIAL SLOAN-KETTERING CANCER CENTER IRB PROTOCOL

IRB#: 12-006A(5)

Hypothesis 1: The threshold effect for memory will occur significantly sooner, i.e. at lower drug concentrations, than the threshold effect for sedation, as illustrated in Fig 2 (the threshold for memory effect is illustrated by the light gray curves in the Figures, and for sedation by the dark curves).

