11.0 BIOSTATISTICS

Overview. This study is a pilot project to separately examine the *amnesic* and the *sedative* effects of the drug propofol. The plan is to recruit a pilot sample of 40 children who will undergo sedation as part of their clinical management and give them a memory encoding task during propofol infusion to measure the effects of *sedation*. The mere task of naming a picture will encode that picture into memory. When the anesthesia has worn off (at approximately 1 hour later), children will be given a memory recognition task to measure the *amnesic* effects of propofol. We will also recruit a total of 30 children who will not undergo sedation to serve as a control group. This brings out total number of participants to 70.

Analytic Plans for the Specific Aims:

Aim 1: The primary objective is to determine the feasibility of using the visual picture naming task in pediatric patients in the clinical setting. Feasibility will be defined as, at the conclusion of the study, 25 or more of the pilot sample of 30 (control) or 35 (propofol) per group complete the recognition memory task and yield usable parameter estimates for the psychophysics function. The probability of declaring the study design feasible is 0.51 when the true population feasibility is 0.70; and the probability of a feasible study increases to 0.92 when the true population feasibility is 0.80.

Descriptive statistics will be sought to examine study feasibility. A running tally of the number of recruited participants will be kept to monitor the recruitment numbers during the anticipated 4 – 6 months study period. Due to the complex nature of this research, many factors affect study feasibility. It would be impractical and unrealistic to set an a priori feasibility target. Rather, we will monitor several factors, including patient volume, rate of study consent, the proportion of patients who can complete the experimental tasks and the practicality of fitting the psychophysical Weibul model described below. Study feasibility will be evaluated holistically at the end of the study by the study investigators.

As for the minimally sufficient number of responses, the 10-events-per-parameter rule of thumb may apply here. (34) Although that rule was developed for logistic regression, which may or may not be too restrictive for the SAS NL MIXED procedure we intend to use to fit the threshold functions.

MEMORIAL SLOAN-KETTERING CANCER CENTER IRB PROTOCOL

IRB#: 12-006A(5)

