Calculations of the sedation and memory thresholds. The overall statistical paradigm will involve non-linear regression modeling to estimate $G(x)$ functions for the memory and sedation curves for each child in order to address the main hypothesis:

"The threshold effect for memory will occur significantly sooner, i.e. at lower drug concentrations, than the threshold effect for sedation".

Sample Size Considerations. The proposed pilot sample of 35 children accrued to the propofol group is primarily determined by our plan to complete the study within 4-6 months. In our experience we have a pool of approximately 10 children who undergo anesthesia for clinical scans each week who would meet the eligibility criteria. Among them an anticipated 50% would agree to participate in this study. If half of these (2-3/week) produce data of sufficient quality to be able to perform curve fitting as described above, we expect to complete recruitment within 5 months.

A sample of 35 children will also yield an 80% power in a one-sample t-test against the null that the difference in the sedation and memory thresholds is zero (null $\sim N(0, 1)$), assuming a two-sided Type-I error rate of 0.05, and an alternative population distribution with a mean of 0.50 and a standard deviation of 1.0. The statistical power was estimated by the G*Power computer program.

MEMORIAL SLOAN-KETTERING CANCER CENTER IRB PROTOCOL

IRB#: 12-006A(5)

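### Section 11.0 uses 35 propofol children as an analysable number for power, as a pre-loss number in Aim 1, and gives 40 in the Overview; the figures cannot all hold

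*Combined protocol and SAP*

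**What the plan says.** All the figures come from Section 11.0 (Biostatistics), apart from one related definition in Section 2.0.

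- **Overview.** "The plan is to recruit a pilot sample of 40 children who will undergo sedation", plus 30 unsedated controls. "This brings out total number of participants to 70".
- **Aim 1.** The design is feasible if "25 or more of the pilot sample of 30 (control) or 35 (propofol) per group complete the recognition memory task" and give usable parameter estimates. "The probability of declaring the study design feasible is 0.51 when the true population feasibility is 0.70", rising to 0.92 at a true rate of 0.80.
- **Sample Size Considerations, accrual.** "The proposed pilot sample of 35 children accrued to the propofol group" is set mainly by the 4 to 6 month timetable. About 10 eligible children a week are expected, of whom half consent. "If half of these (2-3/week) produce data of sufficient quality to be able to perform curve fitting as described above", recruitment should finish within 5 months.
- **Sample Size Considerations, power.** "A sample of 35 children will also yield an 80% power in a one-sample t-test" of the sedation-minus-memory threshold difference against zero, two-sided 0.05, mean 0.50, SD 1.0.
- **Section 2.0.** Feasibility is the ability to "accrue an average of 2 patients a week who successfully name and recognize sufficient numbers of pictures" for both thresholds to be determined in each child.

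The section contains no allowance for loss and does not explain why the propofol group is 40 in one place and 35 in the others.

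**The concern.** The number 35 has two roles that conflict. In the power statement it has to be the number of children who each contribute a threshold difference, because a child lacking either threshold adds nothing to the t-test. In Aim 1 it is the denominator from which children are lost, with 25 as the minimum that must remain. It cannot be both unless almost no child is lost. The plan expects losses: Section 9.0 warns that the software may fail to give a stable threshold for a child, Section 10.0 withdraws children who cannot do either task, and the accrual projection assumes that only half of consenting children give fittable data.

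Three things are at stake: the power claimed for Hypothesis 1, the probabilities attached to the Aim 1 rule, and the point at which propofol accrual stops (35 enrolled, 40 enrolled, or 35 usable).

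**Working it through.** **Inputs** (all Section 11.0): one-sample t-test, two-sided alpha 0.05, d = 0.50/1.0 = 0.5; Aim 1 cut-off 25, usable rates 0.70 and 0.80; propofol numbers 35 and 40; controls 30; projected usable yield one half. The 0.70 and 0.80 are Aim 1 operating points, not forecasts.

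**1. Reproduce the power.** Power = P(|T| > t(0.975, n−1)), where T is noncentral t with n−1 degrees of freedom and noncentrality 0.5√n. At n = 35 the noncentrality is 2.958, the critical value 2.032 and the power 0.820. At n = 34 it is 0.808 and at n = 33 it is 0.795. The stated 80% is therefore correct for 34 to 35 analysable children.

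**2. Reproduce the Aim 1 probabilities.** P(X ≥ 25) with X ~ Binomial(n, p):

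| n | p = 0.70 | p = 0.80 |
|---|---|---|
| 34 | 0.406 | 0.875 |
| 35 | 0.510 | 0.925 |
| 36 | 0.609 | 0.958 |
| 40 | 0.885 | 0.997 |

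Only n = 35 gives the stated 0.51 and 0.92 (0.925, apparently truncated). No other n from 30 to 41 matches, so Aim 1 treats 35 as the number before loss.

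**3. Check the total.** 40 + 30 = 70, whereas 35 + 30 = 65. The Overview's total needs 40.

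**4. If 35 (or 40) is enrolled.** Power by usable children is 0.72 at 28, 0.67 at 25, and 0.49 to 0.52 at 17 to 18. Averaging over X ~ Binomial(N, usable rate):

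| Enrolled N | Usable rate | Average power | P(X ≥ 25) |
|---|---|---|---|
| 35 | 0.80 | 0.72 | 0.925 |
| 35 | 0.70 | 0.66 | 0.510 |
| 35 | 0.50 | 0.50 | 0.008 |
| 40 | 0.80 | 0.78 | 0.997 |
| 40 | 0.70 | 0.72 | 0.885 |
| 40 | 0.50 | 0.56 | 0.077 |

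None of these reaches 80% power.

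**5. If 35 is evaluable.** The 80% stands, but 25 of 35 is then met automatically and 0.51 and 0.92 describe nothing. Expected enrolment is 35/0.80 ≈ 44, 35/0.70 = 50 or 35/0.50 = 70. P(X ≥ 25) at those enrolments is 0.9999, 0.999 and 0.994, so a cut-off of 25 no longer discriminates.

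**6. Which reading does the timetable favour?** Ten eligible a week with half consenting gives 5 a week. Enrolling 35 at that rate takes 35/5 = 7 weeks. Collecting 35 usable at 2 to 3 a week takes 35/3 = 11.7 to 35/2 = 17.5 weeks, closer to the projected 5 months. Section 2.0 also applies accrual to children whose data suffice. Both lean towards evaluable, but neither settles it.

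**The case against.** The best case for the plan has four parts.

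- **Power is stated conditionally.** A power statement is normally read as conditional on the number analysed, and on that basis 80% at 35 is right. This is true of the t-test calculation. It does not help Aim 1, which uses the same 35 before loss, or the text that describes 35 as accrued.
- **40 recruited and 35 usable.** A loss of 5/40 = 12.5% would preserve the 40, the 70 and the 80%. The plan does not say this. It implies 87.5% usable against a projected one half, and it leaves 0.51 and 0.92 unexplained.
- **Two stages of loss.** Data good enough to attempt a fit are not the same as a successful fit. If 35 means children with fittable data, 25 of 35 is not automatic and 0.51 and 0.92 could apply. The 80% would then again need nearly all 35 fits to succeed, so the conflict remains.
- **Little depends on these figures.** This is a pilot sized mainly by timetable. Section 9.0 calls it premature to expect a reliable difference, and Section 11.0 leaves feasibility to a holistic judgement at the end. This stands and limits the weight of the point. It does not make the published figures consistent.

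The lowest figures (50% power, 0.8% chance of reaching 25) hold only if 35 is enrolled and the projected one half is taken as the Aim 1 success rate. The timetable leans away from that reading.

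**Conclusion.** The point holds. The t-test arithmetic and the binomial arithmetic are each correct for 35, but for different meanings of 35, and the Overview's 40 and 70 agree with neither Aim 1 nor the sample-size text. None of the readings considered keeps every stated figure.

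If 35 is enrolled, a study that just meets its own cut-off of 25 has 67% power. Average power is 66% to 72% at usable rates of 70% to 80%, and 50% at one half. The size depends on the true usable rate, which the plan does not establish, and on the stated standardised effect of 0.5. If 35 is evaluable, the power stands but the Aim 1 probabilities and cut-off need replacing. The sponsor should correct this. It affects the power claim and the operating characteristics, and does not undermine feasibility as the study's aim.

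**What to change.** State whether 35 is enrolled or evaluable, and use one propofol number in the Overview (with its total), Aim 1 and Sample Size Considerations. Then follow the matching route.

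- **35 enrolled (cheapest).** Correct the total to 65, keep 0.51 and 0.92 for the propofol group only, and replace the power sentence with, for example: *Power is about 82% if all 35 enrolled children yield both thresholds, 72% with 28, 67% at the feasibility minimum of 25, and about 50% with 17 to 18.* The cost is wording and a less favourable stated power, with no extra patients.
- **40 enrolled.** Keep 70. Restate average power as about 78%, 72% and 56% at 80%, 70% and 50% usable, and the Aim 1 probabilities at a cut-off of 25 as 0.88 (rate 0.70) and 0.997 (rate 0.80). This is also wording only.
- **35 evaluable.** Keep the 80%, say that unusable children are replaced, give the implied enrolment (about 44, 50 or 70), and reset the cut-off and its probabilities on the enrolled number. This costs about 4, 10 or 30 enrolments above the Overview's 40. Seventy enrolments take 70/5 = 14 weeks at 5 consenting a week, but 70/2 = 35 weeks at the lower rate in Section 6.0, which exceeds the 4 to 6 month window. That lower rate is not clearly specific to propofol patients, so 35 weeks is only indicative.

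Where 25 of 30 is kept for controls, give that group its own probabilities: P(X ≥ 25) with n = 30 is 0.08 at a rate of 0.70 and 0.43 at 0.80, not 0.51 and 0.92.
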